The primary objective of this study is to collect and compare clinical outcomes and surgical data using the commercially available ROSA Knee System instrumentation and conventional instrumentation.

This will be done by analysis of validated outcome measurement tools, radiographs and adverse event data.

The assessments will include:

1. Comparison of planned operative vs. actual operative component position
2. Operative workflow efficiency
3. Patient safety based on incidence and frequency of adverse events.
4. Clinical performance measured by overall pain and function, quality of life data, and radiographic parameters.

VI. Study Design

This is a prospective, multicenter clinical study designed to facilitate the collection and evaluation of workflow efficiency, patient pain and function, and adverse event data. This clinical study will include Persona, NexGen, and Vanguard product families using the ROSA Knee System or conventional instrumentation. The primary objective of this study is to collect and compare clinical and surgical data using the commercially available ROSA Knee System instrumentation and conventional instrumentation.

A maximum of 300 subjects are to be competitively enrolled in this study across all sites; a maximum of 10 U.S sites will contribute, with participating sites each enrolling up to 75 implanted knees. Sites will enroll up to 45 patients using The ROSA Knee System and up to 30 patients using Conventional instrumentation; total study enrollment into these arms are not to exceed 180 subjects and 120 subjects respectively. Once the maximum study enrollment has been reached, enrollment at all sites will be closed.

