Investigators will be skilled in total knee arthroplasty and experienced implanting Persona, NexGen, and/or Vanguard knee systems. Each Principal Investigator will be responsible for obtaining Institutional Review Board (IRB) approval as required prior to conducting the study. In order to avoid potential selection bias, each Investigator will offer study participation to each consecutive eligible patient presenting as a candidate for primary total knee arthroplasty using the aforementioned implants. Eligible candidates who express interest in study participation will be offered Informed Consent. All potential study subjects will be required to participate in the Informed Consent process and will not be considered enrolled in the study until the candidate has signed and dated the IRB approved Informed Consent Form. Study data cannot be collected until the candidate has completed the Informed Consent process and signed and dated the IRB approved Informed Consent Form. All study subjects will undergo preoperative clinical evaluations prior to their Robotic-assisted total knee arthroplasty.

At the Sponsor's discretion, the Sponsor may request copies of radiographs for independent radiologic review. The Sponsor may request one central reviewer for all radiographs independent

of the surgeon and institution.

VII. Study Population

The study population for primary statistical analysis will be comprised of males and females who require primary total knee arthroplasty and satisfy the inclusion/exclusion criteria outlined in this section of the protocol. In order to avoid potential selection bias, each Investigator will offer study participation to each consecutive eligible patient presenting as a candidate for primary total knee arthroplasty using the commercially available (FDA cleared) Persona, Vanguard, and NexGen knee systems. Eligible candidates who express interest in study participation will be offered Informed Consent. The inclusion/exclusion CRF should not be completed until the study-specific consent form has been completed.

a. Inclusion Criteria:

1. Patient is a minimum of 18 years of age
2. Independent of study participation, patient is a candidate for commercially available *Persona, NexGen, or Vanguard* knee components implanted in accordance with product labeling
3. Patient has participated in the study-related Informed Consent Process

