NexGen's Primary TKA components in this study will include both fixed and mobile bearing configurations. NexGen accommodates both Cruciate Retaining (CR) and Posterior Stabilized constraint options. The NexGen Flex knee offers patients a larger range of active flexion, accommodating deep flexion up to 155 degrees.

c. Vanguard[®] Knee System

The Vanguard Knee System offers an entire spectrum of knee stability, featuring both Cruciate Retaining (CR) and Posterior Stabilized (PS) femoral stabilization options. Component variation includes ten femoral component sizes, nine tibial component sizes, and five levels of bearing constraints.

IX. Study Procedures

a. Offer Study Participation

Study participation will be offered to each consecutive eligible patient presenting as a potential candidate for total knee arthroplasty using the commercially available ROSA Knee System. An **Enrollment/Informed Consent Log** (Appendix C) will be completed to document all individuals screened as potential candidates for the study. Eligible candidates who express interest in study participation will be offered Informed Consent. Prior to patient involvement in the study, the patient must participate in the Informed Consent process and sign and date the IRB or EC approved Informed Consent.

b. Informed Consent Process

For candidates that express interest, the Investigator or Designee will describe relevant study information, including the purpose, procedures, possible risks, and potential benefits associated with study participation. The Investigator or Designee will also review, along with the candidates, the Informed Consent approved by both the governing IRB or EC and the study Sponsor.

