A **Subject Identification/Informed Consent Log** (Appendix C) will be maintained at the site throughout the course of the study. The purpose of the log is to provide documentation that all enrolled study subjects underwent the Informed Consent process, and signed and dated the IRB or EC approved Informed Consent. All candidates who sign and date the approved Informed Consent for the study must be entered in the log. If a subject signs and dates additional Informed Consent(s) after enrollment (e.g., due to a protocol amendment, protocol revisions, etc.), subsequent signings will also be recorded in the log. The **Subject Identification/Informed Consent** will be filed in the site Regulatory Binder for the study. The proposed date of surgery for each subject will be added to the log. The subject will be considered an active study subject after receiving the study device during surgery. In the event that a subject does not receive the study device at the time of surgery, a **Study Completion** form must be submitted and this will be documented as a screen failure.

d. Subject Enrollment

Once the Informed Consent has been signed and dated by the subject, the subject will be considered enrolled in the study. Robotic and conventional patients should be enrolled using a consecutive and concurrent approach. A unique case identification number (Case ID) will be assigned to each participating subject. This unique case ID number will be used throughout the study for identification. Case ID numbers will be assigned consecutively in ascending order per site, with the starting number for a given site defined by the Sponsor. In the event that the subject does not receive the study device at the time of surgery, the subject will be considered a screen failure and documented on a **Study Completion** form (see above). In the occurrence of a screen failure, the surgeon may have the option to enroll an additional patient as long as the subject did not receive the study device.

e. Monitor Log

The **Site Monitoring Visit Log** (Appendix C) will be maintained throughout the course of the study. The log will contain the visit date, monitor name/signature and the purpose of the visit (i.e. site initiation, onsite interim monitoring (as applicable), site close-out, etc.). The site monitoring visit log will be filed in the site Regulatory Binder for the study.

f. Delegation of Authority (Site Signature Log)

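### The enrolment caps do not put the concurrent-enrolment rule into operation, so arm can be confounded with site and calendar time, and no stratified comparison is planned

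*Combined protocol and SAP*

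**What the plan says.** Section VI makes the comparison of ROSA and conventional instrumentation the primary objective and then sets the enrolment limits:

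- Study total: "A maximum of 300 subjects are to be competitively enrolled in this study across all sites".
- Sites: "a maximum of 10 U.S sites will contribute, with participating sites each enrolling up to 75 implanted knees".
- Arms within a site: "Sites will enroll up to 45 patients using The ROSA Knee System and up to 30 patients using Conventional instrumentation".
- Arms across the study: "total study enrollment into these arms are not to exceed 180 subjects and 120 subjects respectively".
- Closure: "Once the maximum study enrollment has been reached, enrollment at all sites will be closed".

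Timing is covered in Section IX.d: "Robotic and conventional patients should be enrolled using a consecutive and concurrent approach". It does not say whether this applies within a site or across the study, or over what period.

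Sections VI and VII add that "each Investigator will offer study participation to each consecutive eligible patient presenting as a candidate for primary total knee arthroplasty", without saying how the instrument is then chosen. Section IX.a words the same offer around a "candidate for total knee arthroplasty using the commercially available ROSA Knee System", so it names only one arm.

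Section XII.A plans descriptive summaries with 95% confidence intervals, plus subgroups by indication. It mentions neither site nor calendar period. Section XII.B states that there are no hypotheses and that sample size is capped by a ceiling per site.

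**The concern.** Every number in Section VI is a maximum. There is no minimum per arm, no within-site ratio, and no statement of what happens to one arm when the other is full. The sentence in IX.d is the only safeguard that links the arms in time. It is phrased as a recommendation, and the caps do not enforce it.

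This matters because the protocol itself describes outcomes that vary by surgeon and with experience. Section IV names differences between surgeons and a learning curve as shortcomings of current practice. Section IX.i leaves rehabilitation to the investigator. Investigators read the radiographs, and central review is at the sponsor's discretion. The Synopsis expects 12 to 18 months of enrolment.

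Knees with no counterpart in the other arm at the same site and in the same period carry those differences into the arm contrast. A pooled summary cannot separate them from an effect of the instrument, and a larger sample does not help. Section XII foresees use of the summaries in regulatory submissions and publications.

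**Working it through.** **1. The plan's own figures.** 180 + 120 = 300 and 45 + 30 = 75, both as stated. The ratio is 1.5 to 1 at both levels (180/120 and 45/30). The caps are consistent with each other.

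**2. The single-arm tail.** Reaching 300 requires exactly 180 ROSA and 120 conventional knees. Let p be the ROSA share of recruitment, assumed steady (the documents give no share). The first cap fills after min(180/p, 120/(1 − p)) knees. All remaining knees up to 300 belong to the other arm.

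| ROSA share p (assumed) | First cap fills after | Remaining knees | Share of the late arm |
|---|---|---|---|
| 50% | 120/0.5 = 240 (conventional) | 60, all ROSA | 60/180 = 33% |
| 60% | 300 (both together) | 0 | none |
| 70% | 180/0.7 ≈ 257 (ROSA) | about 43, all conventional | 43/120 ≈ 36% |
| 80% | 180/0.8 = 225 (ROSA) | 75, all conventional | 75/120 = 62.5% |

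The same happens within a site. At 50:50 the conventional cap of 30 fills after 30/0.5 = 60 knees, which leaves up to 75 − 60 = 15 ROSA-only knees.

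**3. The worst case on site.** Four ROSA-only sites give 4 × 45 = 180. Four conventional-only sites give 4 × 30 = 120. That is 300 knees at 8 of the 10 permitted sites, within every numerical cap, with arm and site completely confounded.

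**4. Size of the worst case.** Work in units of the outcome SD, with intraclass correlation ρ between patients of one site. The documents give no value, so 0.01 to 0.10 is an assumption.

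- Independent patients: variance = 1/180 + 1/120 = 0.01389, SE 0.118.
- Single-arm sites: variance = (1 + 44ρ)/180 + (1 + 29ρ)/120.
- Both arms at every site in a 3:2 ratio, compared within site: variance = (1 − ρ)(1/180 + 1/120), because additive site effects cancel.
- Coverage of a nominal 95% interval that ignores site, under single-arm sites: 2Φ(1.96/√ratio) − 1.

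| ρ (assumed) | SE, single-arm sites | Variance ratio to independent patients | Coverage of nominal 95% interval | SE, within-site contrast |
|---|---|---|---|---|
| 0.01 | 0.137 | 1.35 | 91% | 0.117 |
| 0.02 | 0.154 | 1.70 | 87% | 0.117 |
| 0.05 | 0.195 | 2.75 | 76% | 0.115 |
| 0.10 | 0.250 | 4.50 | 64% | 0.112 |

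For ρ = 0.10: 5.4/180 + 3.9/120 = 0.0300 + 0.0325 = 0.0625, and 0.0625/0.01389 = 4.5. These figures treat site effects as random noise. A systematic difference between the sites that use each instrument would add bias on top.

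**The case against.** A reader might infer that Sections VI and IX.d contradict each other and cannot both be followed. The documents do not support that. One section sets ceilings and the other sets timing; recruiting 3:2 at every site satisfies both, and the caps are built in that ratio. The only near-conflict is the tail after one cap fills: enrolment stays open towards 300, but concurrent enrolment is no longer possible.

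Two other strong readings also fail. Running one arm after the other fits the caps, but goes against IX.d. A one-arm study would stop at 180 or 120 knees and defeat the stated comparison.

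It is also fair to say that the eight-site layout is an extreme. It fits the protocol as a whole only if concurrent is read as study-wide, which the text leaves open. At an intraclass correlation of 0.01 the SE rises only from 0.118 to 0.137. The sponsor may also appoint one central reader for all radiographs, which would remove one source of site difference.

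Finally, the study tests no hypothesis and reports descriptively. That lowers the stakes for power, but not for bias: a descriptive arm difference still misleads if arm tracks site or period. What stands is the gap. Concurrent is undefined, no rule covers one arm filling first, and no site or period stratification is planned for the comparison that the study exists to make.

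**Conclusion.** The point holds as a gap in the plan. Arm *can* be confounded with site and calendar time; nothing in the documents shows that it has been.

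The likelier form is the single-arm tail, which needs no unusual conduct by any site. At assumed steady ROSA shares of 50% to 80%, other than 60%, it covers roughly 43 to 75 of 300 knees in the three cases worked. It would be shorter if enrolment stops below 300, which is a ceiling and not a target. The worst case is complete site-arm separation, with a variance ratio of 1.35 to 4.5 at an assumed intraclass correlation of 0.01 to 0.10.

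The cap arithmetic comes from the documents. The recruitment shares and intraclass correlations do not.

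**What to change.** - **Section XII, main comparison.** Form the ROSA-conventional comparison within site: the arm difference at each site, combined across sites that enrolled both arms, with a 95% confidence interval.
- **Section XII, sensitivity analysis.** Repeat it with only the subjects operated on, at each site, between the later of the two arms' first-case dates and the earlier of their last-case dates. This addresses calendar time, which the site-stratified estimate alone does not.
- **Section XII, single-arm sites.** Report them only in the per-arm and safety summaries.
- **Section IX.d.** State that concurrent means within site.

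The cost is wording in two sections. Knees from single-arm sites leave the comparative tables, so the comparison may rest on fewer than 300 knees. The IX.d change may need IRB or EC approval where local rules require it.

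Closing enrolment as soon as one arm fills is not needed. On the shares above it would give up about 43 to 75 knees, and it would not prevent single-arm sites. The within-site comparison does not remove differences between patients chosen for each instrument at the same site, since the protocol has no rule for that choice.

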Candidates should be made aware that any and all data collected electronically within the ROSA Knee System will be made available to the sponsor for research related purposes. Candidates shall have sufficient time to read and understand the IRB or EC approved Informed Consent and discuss whether they wish to participate in the study. Candidates will be asked to acknowledge whether all of their questions and concerns have been addressed to their satisfaction. Any questions that candidates may have will be addressed appropriately by the Investigator or Designee. Candidates will be further instructed that they are free to obtain additional information from the Investigator or Designee at any time, that they are free to decline participation, and that they are free to withdraw their consent and discontinue their participation at any time without prejudice.

After completing the Informed Consent process, candidates who agree to enter the study must sign and date the IRB or EC approved Informed Consent. The Informed Consent must be signed and dated prior to the date of the study surgery.

A copy of the signed Informed Consent must be provided to the study subject. The original signed Informed Consent is to be filed in the subject's medical record, study subject binder, or regulatory binder.

Study data will not be collected until the Informed Consent has been signed and dated. If the candidate does not wish to participate (does not sign and date the Informed Consent), data for that candidate will not be collected for this study.

c. Informed Consent and Subject Identification Log

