Potential adverse events associated with total knee arthroplasty include, but are not limited to:

- Wear of the polyethylene articulating surface
- Progressive bone resorption (osteolysis) as a result of foreign-body reaction to wear debris
- Loosening of the prosthetic knee components
- Fracture/damage of the prosthetic knee components
- Soft tissue impingement or damage
- Dislocation and/or joint instability
- Malalignment of the prosthetic knee components
- Bone fracture
- Nerve damage
- Swelling
- Infection
- Leg length discrepancies
- Poor range of motion
- Delayed wound healing
- Temporary or permanent neuropathies
- Pain related to knee arthroplasty and placement of NavitrackERs
- Cardiovascular disorders including venous thrombosis, pulmonary embolism, or myocardial infarction
- Histological reactions resulting in inflammation
- Metal sensitivity
- Corrosion of metal components (the significance and long-term implications are uncertain and await further clinical evidence and evaluation)

Minimization of Risk

Although the total knee implants being used in this study are not the study device, complications can still occur. Complications and/or failure of prosthetic implants are more likely to occur in patients with unrealistic functional expectations, heavy patients, physically active patients, and/or with patients who fail to follow through with the required rehabilitation program. Physical activity or trauma can result in loosening, wear, and/or fracture of the implant. The patient must be counseled about the capabilities of the implant and the impact it will have on his or her lifestyle. The patient must be instructed about all postoperative restrictions, particularly those related to occupational and sports activities and about the possibility that the implant or its components may wear out, fail or need to be replaced. The implant may not last the rest of the patient's life, or any particular length of time. Because prosthetic implants are not as strong, reliable, or durable as natural, healthy tissues/bones, all such devices may need to be replaced at some point.

XII. Statistical Considerations

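### Receipt of the study device decides who stays in the study after consent, but the term has two incompatible meanings, and the infrared note adds an exit that appears confined to planned ROSA cases

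*Combined protocol and SAP*

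**What the plan says.** **Timing.** Section IX.b: "The Informed Consent must be signed and dated prior to the date of the study surgery". Section IX.d: "Once the Informed Consent has been signed and dated by the subject, the subject will be considered enrolled in the study". Anything that happens in the operating room therefore happens to an enrolled subject.

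**Status rules.** Section IX.c: "The subject will be considered an active study subject after receiving the study device during surgery". Under Section IX.d, a subject who "does not receive the study device at the time of surgery, the subject will be considered a screen failure". After a screen failure, "the surgeon may have the option to enroll an additional patient as long as the subject did not receive the study device".

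**The term.** No section defines it. Section XI.B (Minimization of Risk) says: "Although the total knee implants being used in this study are not the study device, complications can still occur". The synopsis in Section II names the ROSA Knee System as the testing article. Against this, Sections IX.j and X.D.8 end participation on a revision that takes out a study device, and Section X.E.3 has an adverse event outcome for such a removal. Section X.D.3 ties study exit at revision to femoral or tibial components and a prosthesis-removed status. Section VIII, headed as study device information, covers ROSA and the implants together.

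**Infrared note.** Sections II and VII.b stop a subject's participation, with a Study Completion form, if infrared interference is found near the NavitrackERs during surgical preparation.

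**Ceilings.** Section VI allows 300 subjects in all, with "participating sites each enrolling up to 75 implanted knees"; "total study enrollment into these arms are not to exceed 180 subjects and 120 subjects respectively".

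**The concern.** The primary objective (Sections V and VI) is to compare ROSA with conventional instrumentation. A rule that removes and replaces enrolled subjects according to what happened at surgery can change who is compared, and can do so unequally between the groups. Here the rule turns on a term that the protocol contradicts. With up to 10 sites, one could drop and replace a robotic case finished with conventional instruments while another keeps following it, each with a textual basis.

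The infrared note raises the same issue by another route. It ends participation after consent and, as far as the documents show, can apply to only one group. The safety and 1-year data of any such subject who goes on to surgery would be missing.

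There is a smaller consequence for safety data. Section X.D.2 has each adverse event rated for its relationship to the study device. On the ROSA meaning, it is unclear what that field should hold for a conventional subject.

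**Working it through.** There is no power or sample size calculation to reproduce: Section XII.B states that there are no hypotheses. The check is to apply the rules under each meaning and then count.

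**Step 1. Apply Sections IX.c, IX.d and VII.b to each kind of consented subject.**

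| Consented subject | Study device = ROSA | Study device = implant |
|---|---|---|
| ROSA case completed with ROSA | Active | Active |
| Conventional case, knee implanted | Screen failure, replaceable | Active |
| Planned ROSA case completed conventionally | Screen failure, replaceable | Active, not replaceable |
| Infrared event, knee then implanted without ROSA | Screen failure, replaceable; also out under VII.b | Active under IX.c, but out under VII.b |
| No study surgery | Screen failure, replaceable | Screen failure, replaceable |

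The two meanings disagree in three of the five rows. The fourth row stays contradictory on the implant meaning, so choosing that meaning does not settle the infrared note. The documents do not say whether an infrared case goes on to surgery; that row assumes it does.

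**Step 2. Is the infrared event confined to planned ROSA cases?** The note is worded for any subject. Section VII.b excludes use of guidance systems, so a conventional case should have no trackers. Section XI introduces its risk list as that of the robotic procedure, and the list in XI.B includes tracker placement. Confinement to ROSA cases is a reasonable inference, not a stated fact.

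**Step 3. Count at the ceilings.** The arm ceilings sum to the study ceiling: 180 + 120 = 300. On the ROSA meaning at most 180 subjects can be active, and 120/300 = 40% would be screen failures. On the implant meaning all 300 can be active.

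If both arms filled and k screen failures were replaced, there would be 300 + k enrolled subjects if screen failures do not count toward the ceiling, or at most 300 − k active subjects if they do. Counting enrollment from consent (IX.d) points to the second; counting sites in implanted knees (VI) points to the first. These are maxima, so no target is missed either way.

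**Step 4. How large could a one-sided exit be?** The documents give no exit rate and no outcome difference. Assume that a share f of the 180 planned ROSA cases exits and that their mean outcome differs by d standard deviations (SD) from those who stay. The ROSA mean then shifts by f × d.

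- Exits: f = 1% gives 1.8 subjects, 5% gives 9, and 10% gives 18.
- Shift: 0.02 × 0.25 = 0.005 SD; 0.05 × 0.5 = 0.025 SD; 0.10 × 1.0 = 0.10 SD.
- Standard error of the difference between arms, at 180 and 120: √(1/180 + 1/120) = 0.118 SD.

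Over this assumed range the shift stays below one standard error. The sign of d is unknown.

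**The case against.** The strongest reply is that any site will read the term as the implant. That meaning fits receipt during surgery, the count in implanted knees and removal at revision, and it keeps converted cases in. The only sentence denying it is an introductory clause in a risk paragraph. Much of this stands: the implant meaning is the workable one and probably the intended one. It does not remove the point. That clause is the only direct statement of what the study device is not, and Section II names ROSA as the testing article. Two passages are also still worded for a ROSA-only study: Section IX.a on offering participation, and the preoperative evaluation sentence in Section VI.

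A reader might infer that the plan discards the whole conventional arm. It does not: Section VI gives that arm its own ceiling, and the literal result shows a drafting conflict, not an intention.

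A reader might also infer that adverse events in conventional subjects go uncaptured. Section X.E.1 contradicts this. Its definition covers events related to the comparator and to the procedures, and an adverse device effect is tied to any medical device. Only the relatedness field is ambiguous.

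It is fair to add that the infrared trigger, as described, is not a patient characteristic, and that exits are already documented on Study Completion forms. Both points limit the likely bias. Neither says how such subjects are counted or reported, and Section XII plans no summary of them.

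**Conclusion.** The point holds and should be fixed. A contradictory term controls active status, screen failure and replacement after enrollment. Separately, the infrared note can remove a subject whom Section IX.c, on the implant meaning, makes active. Together they allow a post-enrollment exclusion that may fall on the ROSA side only.

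The size and direction of any effect on the comparison cannot be derived from the documents. On the assumed rates above it is probably small. A reader might infer that the exits flatter ROSA, but nothing in the documents links an infrared event or a conversion to outcome, so that is not supported. Nor is any power or precision figure affected, because the study is descriptive and its sample sizes are ceilings.

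The conclusion rests on one inference (NavitrackERs are used only in planned ROSA cases) and one assumption (some infrared cases still have the knee implanted). The contradiction in the term itself needs neither.

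**What to change.** 1. Define the study device once, saying what it means in each group, and reconcile Sections II, VII.b, VIII, IX.c, IX.d, IX.j, X.D.2, X.D.8, X.E.3 and XI.B with that definition. State what the adverse event relatedness field refers to for a conventional subject.
2. Limit screen failure and replacement to consented subjects who have no study surgery, and state whether they count toward the 180, 120 and 300 maxima.
3. Reconcile the infrared note with Section IX.c so that a consented subject who goes on to have the knee implanted stays in data collection. This does not change how surgery is done.
4. Record planned and actual instrumentation for every subject. The operative and surgical device forms in Section III, and the ROSA planning data that Section X.B.1 lets the sponsor extract, may already supply part of this. The only planning form listed by name is for conventional cases.
5. Add one table to Section XII giving conversions, post-consent exits and replacements, with reasons, by planned group.

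The cost is wording changes, one table, possibly one data field, and follow-up of a few more subjects, whose number cannot be derived from the documents.
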